Medical review of medical history and AEs will ascertain thromboembolic events for analysis.

Normalization of Bilirubin

The normalization of bilirubin is defined as total bilirubin \leq upper limit of normal (ULN) (specified by the central lab).

Normalization of LDH

The normalization of LDH is defined as LDH value \leq ULN (specified by the central lab).

Normalization of Haptoglobin

The normalization of haptoglobin is defined as haptoglobin above the level of detection.

Hemolytic Breakthrough

Hemolytic breakthrough at any visit is defined as

- A decrease of 2 g/dL or more in Hgb from the last scheduled visit, and
- One of the followings:
 - An increase in LDH from the last scheduled visit,
 - An increase in bilirubin from the last scheduled visit, or
 - A decrease in haptoglobin from the last scheduled visit.

Protocol Prohibited CAD Medications

The following concomitant medications are prohibited during the study treatment period in Part A:

- Rituximab alone or as part of combination therapy
- Cytotoxic drugs (such as fludarabine, bendamustine, ibrutinib, cyclophosphamide)
- Other investigational drug

The efficacy endpoint (estimand) accounting for protocol prohibited CAD medication use will be based on the eCRF questionnaire “Did the subject receive any prohibited medications since the last visit?” at post-baseline visits. The medical review for the list of prohibited medications will be reconciled with the eCRF questionnaire.

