5.1.3. Estimands

Following [International Conference on Harmonisation \(2014\)](#) and [National Research Council \(2010\)](#), the following estimands are considered for efficacy endpoints to provide clarity of what to be estimated and its connection to the trial objectives. [Akacha, et. al. \(2017\)](#) proposed a framework for defining an estimand using three attributes:

- The population of interest;
- The variable to be used for the clinical question, which consists of measurements at a specific timepoint. It could be a composite endpoint that incorporates post-randomization events.
- The measure of intervention effect, which accounts for potential effects of post-randomization events.

A composite estimand will be used for the primary endpoint and a hypothetical estimand will be used for lab parameter defined secondary endpoints. Alternative estimands are also proposed to either assist the interpretation of primary estimand or used for exploratory endpoints.

Composite Estimand

- Population: FAS
- Variable: A composite endpoint: endpoint response criteria, and remain in the study through at least Week 23 visit (i.e., patients who discontinued the study participation prior to Week 23, including those who discontinued prior to Week 5, are considered non-responder)
- Measure of Intervention Effect: Proportion of subjects who respond according to the variable definition

Hypothetical Estimand

- Population: FAS

- Variable: Change from baseline at treatment assessment timepoint (Weeks 23, 25, and 26), where any post-baseline value after transfusion and prohibited medication (from Week 5 to Week 26) is considered missing
- Measure of Intervention Effect: Mean change from baseline, had transfusion and prohibited medications not been available

De-Facto Estimand

- Population: FAS
- Variable: Change from baseline at treatment assessment timepoint (Weeks 23, 25, and 26)
- Measure of Intervention Effect: Mean change from baseline, irrespective of transfusion or prohibited medications

Observed Estimand

- Population: a subset of FAS, subjects who remain in the study through at least the visit of interest (e.g., Week 23) and have at least 1 evaluable parameter or score at target visits.
- Variable: Change from baseline at the visit of interest, or response at the visit of interest
- Measure of Intervention Effect: Mean change from baseline or proportion of subjects who respond, irrespective of transfusion or prohibited medications

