5.2.2. Categorical Variables

Categorical variables will be summarized by counts and percentages. All percentages will be rounded to one decimal place. The percentage will be suppressed when the count is zero. Unless specified otherwise, the denominator for all percentages will be the number of subjects with non-missing data for a given summarization. This number (n) will be included with categorical summaries unless the same variable is also being summarized with descriptive statistics, in which case 'n' will already be provided.

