7.4.1.2. Response Endpoints

The response endpoints include:

- Incidence of solicited symptomatic anemia at EOT
- Incidence of thromboembolic events after the first 5 weeks of study drug administration
- Proportion of subjects with Hgb level of ≥ 12 g/dL at the treatment assessment endpoint
- Proportion of subjects normalizing haptoglobin at the treatment assessment endpoint
- Proportion of subjects normalizing bilirubin at the treatment assessment endpoint
- Proportion of subjects normalizing LDH at the treatment assessment endpoint
- PGIC and change from baseline in PGIS to assess subject's perception of changes in CAD disease burden at last scheduled visit of Part A
- Incidence of disabling circulatory symptoms at last scheduled visit of Part A
- Proportion of subjects normalizing Hgb (≥ 12 g/dL) by visit
- Proportion of subjects achieving 2 g/dL increase in Hgb by visit
- Proportion of subjects normalizing bilirubin by visit
- Proportion of subjects normalizing LDH by visit
- Proportion of subjects normalizing haptoglobin by visit

The endpoints will be summarized for FAS according to [Section 5.2.2](#).

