7.4.1.3. Time-to-Event Endpoints

Time-to-event endpoints include:

- Time to first transfusion after the first 5 weeks of study drug administration
- Time to first transfusion (including those in the first 5 weeks of study drug administration)
- Time to first normalization of bilirubin
- Time to first normalization of LDH
- Time to first normalization of haptoglobin
- Time to first normalization of Hgb level (≥ 12 g/dL)
- Time to first achieving 2 g/dL increase in Hgb level
- Time to first achieving 2 g/dL increase or normalization of Hgb level (≥ 12 g/dL)

The endpoints will be analyzed for FAS according to [Section 5.2.3](#). For subjects who receive a transfusion after Week 5, the time to normalization of lab parameters above will be censored at the time of transfusion.

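### SAP Part A does not remove patients already normal at baseline from the LDH and haptoglobin normalisation analyses, so a value normal before treatment can count as normalisation

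*SAP*

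**What the plan says.** SAP Part A section 5.1.1 defines normalisation of each marker by a single threshold. For LDH, "The normalization of LDH is defined as LDH value" at or below the central laboratory's ULN. For haptoglobin, "The normalization of haptoglobin is defined as haptoglobin above the level of detection". Neither definition mentions the baseline value.

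Section 7.4.1.2 lists "Proportion of subjects normalizing LDH at the treatment assessment endpoint", the matching haptoglobin and bilirubin proportions, and by-visit versions. On population it says "The endpoints will be summarized for FAS according to" section 5.2.2. Section 7.4.1.3 lists "Time to first normalization of LDH" and the same for haptoglobin and bilirubin, and says "The endpoints will be analyzed for FAS according to" section 5.2.3.

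Three other rules narrow these populations:
- Section 7.4.1 applies the Observed Estimand, which section 5.1.3 limits to FAS patients who remain in the study and "have at least 1 evaluable parameter or score at target visits".
- Under section 5.2.2, unless specified otherwise, "the denominator for all percentages will be the number of subjects with non-missing data for a given summarization".
- Section 7.4.1.3 censors time to normalisation at a transfusion after Week 5.

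None of the three depends on whether the marker was abnormal at baseline.

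Protocol section 5.1 requires haemoglobin at or below 10.0 g/dL and bilirubin above the reference range. No criterion sets a level for LDH or haptoglobin. Chronic haemolysis is part of the diagnosis but is not tied to either marker.

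**The concern.** A patient cannot normalise a value that is already normal. As the SAP is worded, a patient with LDH within range on Day 0 and at Weeks 23 to 26 meets the definition and enters the numerator. Read literally, that patient also has a time-to-event outcome at the first normal post-dose value. Haptoglobin is exposed in the same way, because low but detectable haptoglobin on Day 0 already satisfies the definition.

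In a single-arm study no control group would show this up, and a pre-treatment normal value would read as drug effect. Both markers are named protocol endpoints (Protocol section 4.3.3) and belong to the Part A analysis that supports the marketing applications.

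The SAP conditions on baseline elsewhere. Its laboratory shift summary (section 8.2.1.2) takes percentages over patients at risk, meaning those whose baseline was not already low or high. Its clinically significant abnormalities (section 8.2.1.3) must be a worsening from baseline. The normalisation endpoints have no such condition.

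**Working it through.** **Plan's own figure.** The plan states no expected rate or time for LDH or haptoglobin normalisation, so there is nothing on this point to reproduce. Its only sample-size figure, 90% power for the primary endpoint with 20 patients, does not bear on it.

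**Inputs**
- N = 20, the planned enrolment (Protocol section 7.10), taken here as all evaluable.
- m = number normal on the marker at baseline. Not in the documents; varied.
- s = probability that a baseline-normal patient is normal at the treatment assessment. Not in the documents; taken as 1, then 0.9.
- q = probability that a baseline-abnormal patient is normal at the treatment assessment. Not in the documents; varied. The values 30% and 66% are borrowed from the primary endpoint's null and expected responder rates purely as reference points, since neither describes LDH or haptoglobin.

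**Proportion**

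Reported proportion = [m·s + (20 − m)·q] / 20.

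Proportion among patients who could normalise = q.

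Bias = (m/20)(s − q), which becomes (m/20)(1 − q) when s = 1.

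For m = 4 and s = 1:
- q = 30%: 0.20 × 0.70 = 0.14, so 44% is reported instead of 30%.
- q = 66%: 0.20 × 0.34 = 0.068, so 72.8% instead of 66%.
- q = 80%: 0.20 × 0.20 = 0.04, so 84% instead of 80%.

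Bias in percentage points with s = 1:

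| m of 20 | q = 30% | q = 66% | q = 80% |
|---|---|---|---|
| 0 | 0 | 0 | 0 |
| 2 | 7 | 3.4 | 2 |
| 4 | 14 | 6.8 | 4 |
| 6 | 21 | 10.2 | 6 |

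If baseline-normal patients do not all stay normal, the bias shrinks. With s = 0.9, m = 4 and q = 80% it is 0.20 × 0.10 = 2 points. If s were below q it would be negative.

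**Median time**

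Suppose the m patients all have their event at the first assessment. The FAS median is then the (0.5 − m/20)/(1 − m/20) quantile of the time distribution among patients abnormal at baseline:
- m = 2: 0.40/0.90 = 44th percentile
- m = 4: 0.30/0.80 = 37.5th percentile
- m = 6: 0.20/0.70 = 29th percentile

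If the at-risk times were exponential, the FAS median would be 0.85, 0.68 and 0.49 times the at-risk median. Real times fall on a visit grid, so a small m may leave the reported visit unchanged.

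**What else in the plan shows baseline status**
- The SAP's table list (section 12) includes a by-visit shift between non-detectable and detectable haptoglobin. That lets a reader separate the two groups for the haptoglobin proportion, but not for its median time.
- LDH has no counterpart. It is absent from the chemistry tests summarised in section 8.2.1 and from Table 8.

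**The case against.** The strongest reply is that nobody knows whether any patient was normal at baseline. A population with chronic haemolysis, raised bilirubin, haemoglobin at or below 10.0 g/dL and recent transfusion may contain few or none. That stands: the gap in the rule is certain, but the inflation is conditional.

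It can also be said that the word normalising implies a change from abnormal, and that table shells not in these documents may fix the denominator. Neither can be ruled out. But the SAP's explicit definition has no such condition and names the FAS. At best, the handling of baseline-normal patients in the Kaplan-Meier analysis is left open.

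Third, a reader has other evidence. Baseline haemolytic parameters and by-visit changes are summarised, all baseline and derived data are listed, and haptoglobin has its shift table. The main LDH endpoint is the secondary mean change from baseline, from a model that includes the baseline value. All true, and a reason for a low rating. None of it corrects the LDH proportion or either median.

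Finally, the share of patients in the normal range at end of treatment is a legitimate description. It is, provided it is not labelled as normalisation.

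Stronger readings are tempting but unsupported. A reader might infer that the reported figures are inflated as a matter of fact, or that the medians collapse to Week 1. The first needs at least one baseline-normal patient and, for the proportion, s above q. The second needs about half the cohort normal at baseline, which nothing in the documents suggests. A reader might also infer that every FAS patient enters the denominator, but the Observed Estimand and the non-missing rule limit it to evaluable patients.

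**Conclusion.** The point holds in conditional form. By its wording, SAP Part A lets a patient already normal on LDH or haptoglobin count as normalising, and eligibility does not prevent such patients from enrolling. If any do, the median is taken from an earlier percentile of the at-risk distribution. The proportion is inflated when those patients are likelier than the others to be normal at Weeks 23 to 26.

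For m = 4 of 20, all staying normal, the inflation runs from 14 points (q = 30%) through about 7 (q = 66%) to 4 (q = 80%); it is zero for m = 0. Both m and q are assumptions, as is the value of s, and a low q enlarges the effect.

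Bilirubin is less exposed because a raised level is an entry criterion. Protocol section 6.1.1.1 bases eligibility on the first screening results, however, whereas baseline is the last value before dosing.

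The endpoints are exploratory and no formal test is attached to them (SAP section 7.1.1). The primary analysis, its error rate and power, and the secondary analyses are unaffected. Severity is minor.

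**What to change.** For each marker, base the proportion normalising and the time to first normalisation on patients abnormal at baseline: LDH above ULN, haptoglobin not detectable and, for consistency, bilirubin above ULN. Show in each table that denominator and the number already normal at baseline. State in section 7.4.1.3 that patients already normal at baseline are outside the risk set.

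Keep the FAS figure as a supplement labelled as the proportion with values in the normal range (for haptoglobin, with detectable values).

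The change needs a sentence or two in sections 7.4.1.2 and 7.4.1.3 and no new data, since both markers are in the clinical chemistry panel drawn on Day 0. The cost is a smaller n, and so less precision, in exploratory tables that start from about 20 patients.

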7.4.1.2.1. Incidence of Solicited Symptomatic Anemia

Incidence of solicited symptomatic anemia will be summarized by visit descriptively using the FAS. The summaries will be based on observed data only. Proportion of subjects with improvement in anemia symptoms will be summarized by visit. The improvement is defined as at least 1 grade reduction in at least 1 symptom, and no worsening in other remaining symptoms. In addition, proportion of subjects with at least 1 grade decrease will be summarized for each anemia symptom by visit.

7.4.1.2.2. Incidence of Thromboembolic Events after the First 5 Weeks of Study Drug Administration

The adverse event data will be reviewed by internal medical staff to identify all thromboembolic events reported. The detailed listing for all events will be provided including date (study day) of onset, verbatim terms of the event, and the flag whether the event occur after first 5 weeks of study drug administration.

Incidence of thromboembolic events will be calculated as the total number of thromboembolic events after the first 5 weeks of study drug administration divided by the total subject-year of time for observation (i.e., time from Week 5 through Week 26 or EOT visit for subjects who discontinue early). All events from Week 5 through Week 26 or EOT visit for subjects who discontinue early will be included. A 95% exact CI will be provided.

Anti-coagulation medication use will be reviewed and identified based on reported concomitant medications, and will be summarized.

7.4.1.3. Time-to-Event Endpoints

Time-to-event endpoints include:

- Time to first transfusion after the first 5 weeks of study drug administration
- Time to first transfusion (including those in the first 5 weeks of study drug administration)
- Time to first normalization of bilirubin
- Time to first normalization of LDH
- Time to first normalization of haptoglobin
- Time to first normalization of Hgb level (≥ 12 g/dL)
- Time to first achieving 2 g/dL increase in Hgb level
- Time to first achieving 2 g/dL increase or normalization of Hgb level (≥ 12 g/dL)

The endpoints will be analyzed for FAS according to [Section 5.2.3](#). For subjects who receive a transfusion after Week 5, the time to normalization of lab parameters above will be censored at the time of transfusion.

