5.1.1. Definitions

Study Day

Study Day is defined as days relative to the date of first dose of BIVV009, Day 0. In other words, Study Day 1 is Day 0 as defined in the protocol. The start/stop day of events will be calculated as (date of event – date of Study Day 1 + 1) if the date of event is on or after the first dose date, or (date of event – date of Study Day 1) if the date of event is before the first dose date.

Incomplete dates will be imputed for the calculation of study days, unless specified otherwise:

- If missing day only, the start date will be imputed as the first day of the month, while the end date will be imputed as the last day of the month;
- If missing day and month, the start date will be imputed as the first day of the year, while the end date will be imputed as the last day of the year;

Baseline

Baseline measures are defined as the last value prior to the administration of the study drug. If a transfusion occurs during the screening period, the baseline measure must be at least 7 days after the transfusion.

Part A Study Treatment Period

The Part A study treatment period starts at the date of first study drug administration and ends at the date of Week 26 visit if the subject completes Part A study treatment, or at the date of Early Termination (ET)/Safety Follow-up Visit if the subject discontinues the study treatment prior to Week 25.

Visit Windows

Analysis by study visit will utilize the data recorded on the corresponding nominal visit from electronic Case Report Forms (eCRFs). In case of missing data/assessments for a visit, data from an unscheduled visit, or EOT/ET/Safety Follow-up Visit will be used, if the Study Day of such a visit fits in the analytic window defined in [Table 1](#). If multiple values are identified within the analytic window, the one closest to the target study day will be used.

Table 1: Analytic Visit Windows

Visit	Target Study Day	Analytic Visit Window (Study Day)
Baseline (Day 0)	1	≤ 1
Week 1 (Day 7)	8	2 – 15
Week 3 (Day 21)	22	16 – 29
Week 5 (Day 35)	36	30 – 43
Week 7 (Day 49)	50	44 – 57
Week 9 (Day 63)	64	58 – 71
Week 11 (Day 77)	78	72 – 85
Week 13 (Day 91)	92	86 – 99
Week 15 (Day 105)	106	100 – 113
Week 17 (Day 119)	120	114 – 127
Week 19 (Day 133)	134	128 – 141
Week 21 (Day 147)	148	142 – 155
Week 23 (Day 161)	162	156 – 169
Week 25 (Day 175)	176	170 – 179
Week 26 (Day 182; EOT Visit in Part A)	183	180 – 189

Treatment Assessment Timepoint

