5.2.3. Event Time Variables

Time-to-event variables will be summarized using Kaplan-Meier estimate over time, along with median time to event and probability of an event at specific time points. Partial dates will not be imputed, hence considered unknown. In general, for subjects who do not experience the event, the time-to-event will be censored at the study day of last assessment within a study period (Part A or Part B).

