For either estimand, the mean change from baseline in LDH at treatment assessment timepoint, along with its 95% CI, will be estimated by the MMRM model ([Section 5.1.4.1](#)).

Additional sensitivity analyses for hypothetical estimand, similar to those specified for bilirubin, will be performed for the change from baseline in LDH at treatment assessment timepoint.

Additional descriptive analyses will be performed for LDH isoforms.

7.3.4. Number of Transfusions and Number of Units after the First 5 Weeks of Study Drug Administration

The number of transfusions after Week 5 through Week 26 visits will be summarized for the FAS, where the observed data will be used for subjects who discontinue study treatment early in Part A. The number of units transfused during the same period of time will be summarized for subjects who receive at least 1 transfusion.

The transfusions occurring during the first 5 weeks will be listed.

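### Transfusions in Weeks 0–5 have no handling rule in the time-to-event Hgb endpoints, so a rise from donor blood can count as a first 2 g/dL increase

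*SAP*

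**What the plan says.** Section 7.4.1.3 of the Part A SAP lists eight time-to-event endpoints. Three concern Hgb: time to at least 12 g/dL, "Time to first achieving 2 g/dL increase in Hgb level", and time to whichever of these two comes first. One sentence deals with transfusion: "For subjects who receive a transfusion after Week 5, the time to normalization of lab parameters above will be censored at the time of transfusion". Section 5.2.3 adds only that, in general, "for subjects who do not experience the event, the time-to-event will be censored at the study day of last assessment"; it does not mention transfusion.

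The transfusion triggers (Protocol Table 1; Part A SAP Section 3.1.2) apply throughout the 6-month treatment period, with no exemption for the first weeks. The SAP expects that early transfusions may occur. Section 7.3.4 states "The transfusions occurring during the first 5 weeks will be listed", and Section 7.4.1.3 has a separate time-to-first-transfusion endpoint that includes them. For a transfusion during screening, Section 5.1.1 requires that "the baseline measure must be at least 7 days after the transfusion". Post-dose Hgb values have no comparable rule.

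**The concern.** These endpoints start at the first dose and record the first crossing of a threshold. Once a crossing is recorded, a later fall does not undo it. A patient transfused in Week 2 whose next Hgb is 2 g/dL above baseline becomes an early event, although donor blood may have produced the rise. The same transfusion after Week 5 would at most censor the patient.

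The 5-week allowance suits the primary endpoint, which uses the mean Hgb of Weeks 23, 25 and 26, long after early donor blood matters. It does not suit a clock that starts at Day 0. At stake is the description of how quickly Hgb rises on drug. With about 20 patients, a few such events can visibly move the early curve and the median.

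**Working it through.** **1. Figures in the plan.** The documents give no figure for these endpoints. The one design figure concerns the primary endpoint (Protocol Section 7.10): 11/20 needed and 90% power at a true rate of 66%. It reproduces: the exact lower limit is 31.5% for 11/20 and 27.2% for 10/20, and power is 0.897. It has no bearing on this point.

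**2. What the transfusion rule covers.**

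| Endpoint | Transfusion in Weeks 0–5 | Transfusion after Week 5 |
|---|---|---|
| Hgb ≥ 12 g/dL | no rule | censored |
| Rise of 2 g/dL | no rule | unclear: not a normalization |
| Either of the two | no rule | unclear: only one part is a normalization |

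**3. Which thresholds donor blood can reach.** Let B be baseline Hgb, T the value before transfusion, and r the rise still present at the next measurement.

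- The 2 g/dL event needs T + r ≥ B + 2, so r ≥ 2 + (B − T).
- The 12 g/dL event needs r ≥ 12 − T. Transfusion requires T < 9 (symptomatic) or T < 7 (asymptomatic), so r must exceed 3 or 5 g/dL.

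Examples with an assumed r of 2 g/dL (the documents give no value):

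- B = T = 8.5: the next value is 10.5, a change of +2.0, and the event is scored.
- B = 9.5, T = 8.5: the next value is 10.5, a change of +1.0, and there is no event.
- Any permitted T: T + 2 < 11, so 12 g/dL is not reached.

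The exposure therefore lies in the 2 g/dL endpoint and in the 2 g/dL part of the combined endpoint.

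**4. Ceiling.** Suppose k of 20 patients are transfused before Week 5, all cross at the next visit, and nobody has a drug-related event or other censoring by then. The Week 5 event probability as written is k/20: 5% for k = 1, 10% for k = 2, 20% for k = 4, 30% for k = 6. With censoring at transfusion it is 0%.

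**5. Illustration with drug-related events.** The simulation used 20 patients, the protocol visit grid, 2,000 runs per scenario, exponential true times, transfusion at a uniform time in Weeks 0–4.9, and a crossing at the next visit in every transfused patient. The true median in transfused patients is set at twice that of the others. All these inputs are assumptions.

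| True median, others / transfused (weeks) | k | Week 5 probability, as written | Censored at transfusion | Difference (points) | Typical median, as written vs censored (weeks) |
|---|---|---|---|---|---|
| 4 / 8 | 2 | 62% | 57% | 5 | 5 vs 5 |
| 4 / 8 | 4 | 66% | 57% | 9 | 5 vs 5 |
| 4 / 8 | 6 | 70% | 56% | 14 | 3 vs 5 |
| 8 / 16 | 2 | 42% | 35% | 7 | 7 vs 9 |
| 8 / 16 | 4 | 48% | 34% | 14 | 5 vs 9 |
| 8 / 16 | 6 | 55% | 34% | 21 | 5 vs 9 |
| 16 / 32 | 2 | 28% | 19% | 9 | 13 vs 17 |
| 16 / 32 | 4 | 35% | 19% | 16 | 11 vs 17 |
| 16 / 32 | 6 | 44% | 19% | 25 | 7 vs 17 |

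**6. Censoring is not neutral.** Take the 8 / 16 scenario with k = 4. The assumed true Week 5 probability is 1 − 2^(−5/8) = 35.2% in 16 patients and 1 − 2^(−5/16) = 19.5% in 4. Overall this is (16 × 35.2% + 4 × 19.5%)/20 = 32.0%. The censored analysis gives 34%, about 2 points too high; the analysis as written gives 48%, 16 points too high. Censoring is much closer but leans the same way when transfused patients do worse.

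**The case against.** The strongest defence is the declared estimand. Section 7.4.1 places exploratory endpoints under the Observed Estimand, which Section 5.1.3 defines regardless of transfusion. But that definition covers mean change and response proportions, and Section 7.4.1.3 already departs from it by censoring after Week 5. It does not explain why Weeks 0–5 are exempt.

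A second defence is scope, and it stands. The endpoints are exploratory, Section 7.1.1 tests nothing beyond the primary hypothesis, and the two endpoints involving a 2 g/dL rise are not in the protocol's list (Section 4.3.3). Early transfusions are listed, have their own time-to-event endpoint, and are summarised by study period, so a reader of the report could identify affected patients.

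Third, a reader might infer more than the documents support:

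- **That all three Hgb endpoints are equally affected.** Step 3 shows that reaching 12 g/dL needs a rise of more than 3 g/dL.
- **That early transfusion marks the slowest responders.** The trigger is an absolute Hgb level, with symptoms. A symptomatic patient who starts below 9 g/dL qualifies at once, before response can be judged.
- **That the Week 5 proportion is overstated by 10 to 20 points.** For two to four patients this is a ceiling. The rise is measured from baseline rather than from the pre-transfusion value, and Protocol Section 2.2.2 reports rapid correction of anemia in Phase 1b, so some of these patients might reach the event on drug anyway.
- **That the 7-day baseline gap could serve as the rule.** It governs only the baseline after a screening transfusion. Hgb visits are 14 days apart after Day 7, so a transfusion on Day 10 precedes the Day 21 value by 11 days, and a 7-day exclusion would leave that value in.

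**Conclusion.** The point holds as a limited one. The SAP has no rule for transfusions in Weeks 0–5 in its time-to-event Hgb endpoints, and a rise from donor blood can be scored irreversibly as a first 2 g/dL event or as the combined event. The wording also leaves open whether the 2 g/dL endpoint is protected after Week 5. Time to 12 g/dL is much less exposed.

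The direction is clear: shorter times and more early events. The size cannot be determined, because the documents give neither the number of early transfusions nor the Hgb rise per transfusion. The ceiling is 1/20 = 5 points on the Week 5 event probability per affected patient. The differences of 5 to 25 points in the illustration rest wholly on assumed inputs, including that every early transfusion leads to a crossing. The primary endpoint is largely unaffected, and no formal conclusion of the trial depends on these curves. This is a cheap improvement to descriptive analyses.

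**What to change.** Amend the transfusion sentence in Section 7.4.1.3 of the Part A SAP in two ways:

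1. Apply the rule from the first dose of study drug instead of from Week 5.
2. Name all three Hgb endpoints (at least 12 g/dL, rise of 2 g/dL, and either), so that no Hgb value after an on-study transfusion can count as a first event.

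The same sentence governs bilirubin, LDH and haptoglobin, so state whether the earlier start applies to them too.

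Because low Hgb triggers transfusion, this censoring is informative. Add a sensitivity analysis that treats transfusion as a competing event or as failure to achieve the rise. A fixed exclusion window such as 7 days should not be the main rule.

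The cost is small. Transfusions are already recorded at every visit (Protocol Section 6.1.3), so no new data are needed. A few patients are censored early, which loses some precision in descriptive curves. If the Part A database is already locked, report the amended analysis as a labelled sensitivity analysis beside the original.
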